# 8.2.2. Secondary Objectives

## 8.2.2.2. Additional Exclusion Criteria

- 1) Exclude patients with medical claims indicating a diagnosis code for venous thromboembolism (VTE; see Appendix) during the 12 months prior to or on the index date;
- 2) Exclude patients with medical claims indicating a diagnosis or procedure code of transient AF (see Appendix) during the 12 months prior to or on the index date;
- 3) Exclude patients with medical claims indicating pregnancy (see Appendix) during the study period;
- 4) Exclude patients with medical claims indicating hip/knee replacement surgery within 6 weeks prior to the index date;
- 5) Exclude patients with 0 days of follow-up;
- 6) Exclude patients who initiated more than one OAC treatment on the index date.

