For the primary and secondary objectives, the first AF diagnosis date during the identification period will be used as the index date for both ever-treated and never-treated cohorts. Across both ever-treated and never-treated cohorts, all patients will be required to have a  $CHA_2DS_2$ -VASc $\geq 2$  and 12-months of continuous health plan enrollment, with medical and pharmacy benefits before the index date (baseline period). For the primary objective and high-risk subgroup analyses, patients will also be required to have 6-month continuous health plan enrollment, with medical and pharmacy benefits after the index date.

For the primary objective and high-risk subgroup analyses, the following patients will be excluded: an AF diagnosis any time prior to the first AF diagnosis; medical claims indicating a diagnosis or procedure for mitral valvular heart disease or heart valve replacement/transplant;

Do not distribute for purposes outside of specific activities related to development of FDAMAs114 compliant pieces. Content within this protocol is subject to change based on communication planning and input by external review committees.

Apixaban NON-INTERVENTIONAL STUDY PROTOCOL

or use of OACs during the baseline period. For the secondary objective assessing effectiveness, safety, and cost outcomes, patients will be further excluded if they had any of the following: venous thromboembolism; transient AF during the baseline period; pregnancy during the study period; hip/knee replacement surgery within 6 weeks pre-index date; or follow-up period = 0 day. In addition, among patients ever treated with an OAC, those with >1 OAC prescription claim at the index date will be excluded as well.

**Variables:** Baseline demographic and clinical characteristics will include age, gender, race, geographic region, Medicaid dual eligibility, Part-D low income subsidy, Charlson comorbidity index (CCI), CHADS2, CHA2DS2-VASc, HAS-BLED scores, prior bleeding/stroke events, congestive heart failure, diabetes, hypertension, chronic obstructive pulmonary disease, renal disease, myocardial infarction, dyspepsia or stomach discomfort, peripheral arterial disease, transient ischemic attack, coronary artery disease, history of falls, medication use, and index dose of DOAC. Baseline all-cause health care costs and utilization will be included.

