# 8. Research Methods

# 8.1. Study Design

The study will be a longitudinal retrospective cohort analysis using the US fee-for-service (FFS) Medicare database. This database contains data from inpatient departments, outpatient departments, carrier claims, reported drug events, and beneficiaries' enrollment data. The following will be determined and compared between treatment status (treated with apixaban, dabigatran, edoxaban, rivaroxaban, or warfarin and untreated with OAC): outcomes including major bleeding, stroke/SE, and death; and health care costs and resource utilization. The overall study period will be from 01JAN2012-31DEC2016. The study will designate a 12-month baseline period prior to an index identification period (01JAN2013-31DEC2016). The date of first AF diagnosis during the study period will be assigned as the index date.

Figure 1. Study Periods for Primary and High-Risk Subgroup Objectives

(for illustration purposes only, may not be proportional)

Do not distribute for purposes outside of specific activities related to development of FDAMAs114 compliant pieces. Content within this protocol is subject to change based on communication planning and input by external review committees.

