# 8.2.3. Cohorts

Patients eligible according to the above criteria will be assigned to the following cohorts:

Do not distribute for purposes outside of specific activities related to development of FDAMAs114 compliant pieces. Content within this protocol is subject to change based on communication planning and input by external review committees.

Apixaban NON-INTERVENTIONAL STUDY PROTOCOL

- 1) Ever-Treated Cohort: NVAF Patients had ≥1 pharmacy claim for apixaban, dabigatran, edoxaban, rivaroxaban, or warfarin from 01JAN2013-31DEC2016 on or after the first AF diagnosis
  - a. Apixaban cohort: Patients who initiated with apixaban on or after index date
  - b. Dabigatran cohort: Patients who initiated with dabigatran on or after index date
  - c. **Edoxaban cohort:** Patients who initiated with edoxaban on or after index date. Given the small sample size, edoxaban patients will not be included in the secondary clinical and healthcare utilization and costs analyses.
  - d. Rivaroxaban cohort: Patients who initiated with rivaroxaban on or after index date
  - e. Warfarin cohort: Patients who initiated with warfarin on or after index date
- 2) Never-Treated Cohort: NVAF patients with no pharmacy claim for an OAC from 01JAN2013-31DEC2016

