# Time-Varying Cox Regression Models (Secondary Clinical Objectives)

Time-varying Cox models will be used to compare the time to stroke/SE, major bleeding, and death between: 1) treated vs untreated; 2) each OAC vs untreated after inverse probability treatment weighting. Treatment will be used as a time varying covariate, in order to account for the untreated period of an ever-treated patient. Weights generated using IPW will be incorporated.

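### The VTE, hip/knee replacement and dual-OAC exclusions are checked at the first AF diagnosis, although OAC may start up to four years later, so later starts are largely unscreened and bleeding, death and cost contrasts can be confounded

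*Protocol*

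**What the plan says.** **Index date.** The Abstract (Population) states that "the first AF diagnosis date during the identification period will be used as the index date for both ever-treated and never-treated cohorts". Section 8.1 agrees: "The date of first AF diagnosis during the study period will be assigned as the index date".

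**Exclusions.** Section 8.2.2.2 adds criteria for the secondary objectives. Three matter here, and each is tied to that index date:
- VTE: "venous thromboembolism (VTE; see Appendix) during the 12 months prior to or on the index date"
- Joint replacement: "Exclude patients with medical claims indicating hip/knee replacement surgery within 6 weeks prior to the index date"
- Dual start (criterion 6): "Exclude patients who initiated more than one OAC treatment on the index date"

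None of the three is among the exclusions for the primary objective in 8.2.1.2.

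**Exposure.** Section 8.2.3 defines the ever-treated cohort by at least one OAC claim "from 01JAN2013-31DEC2016 on or after the first AF diagnosis". The drug cohorts follow the same pattern, for example "Patients who initiated with apixaban on or after index date". No maximum delay is set and no indication is checked. Section 8.7 (time-varying Cox models) expects delayed starts: "Treatment will be used as a time varying covariate, in order to account for the untreated period of an ever-treated patient".

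**A second date exists.** Table 2 measures time to discontinuation and time to switch from a separate OAC prescription index date. The exclusions do not use it.

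**The concern.** The protocol does not state why these exclusions are there. Their evident purpose is to keep out patients whose anticoagulation is prompted by a VTE or by joint surgery, and to keep the drug cohorts distinct. They do that fully only when OAC starts on the day of the AF diagnosis.

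Take a patient with AF diagnosed in March 2013, untreated, who has a knee replacement in May 2015 and a first OAC fill that week. No exclusion applies. The patient moves from untreated to treated time immediately after surgery, when bleeding, admission and cost may be raised for reasons other than the OAC. A VTE after index works the same way. These outcomes are the subject of secondary objectives 2, 4 and 5.

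The dual-start rule raises a different problem, which is cohort overlap. Two OACs filled together on a first treatment date one month after index do not trigger criterion 6, and the patient then meets two of the drug cohorts in 8.2.3.

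**Working it through.** The plan gives no figure to reproduce on this point. The check is date arithmetic plus a search for another provision that would close the gap.

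**Inputs**
- Identification period 01JAN2013 to 31DEC2016 (8.1, 8.2.3).
- Hip/knee window W = 6 weeks = 42 days (8.2.2.2).
- VTE window W = 12 months = 365 days (8.2.2.2).
- t = days from first AF diagnosis to first OAC fill.

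**Step 1: longest possible delay.** 31DEC2016 minus 01JAN2013 = 1,460 days; 1,460 / 365.25 = 4.0 years.

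**Step 2: how much of the look-back before the OAC start is screened.** A window of length W ending at index overlaps the window of length W ending at the OAC start by W − t days. The share screened is max(0, (W − t)/W).

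| t (days) | Hip/knee, W = 42 | VTE, W = 365 |
|---|---|---|
| 0 | 100% | 100% |
| 14 | 28/42 = 67% | 351/365 = 96% |
| 30 | 12/42 = 29% | 335/365 = 92% |
| 42 | 0% | 323/365 = 88% |
| 90 | 0% | 275/365 = 75% |
| 180 | 0% | 185/365 = 51% |
| 365 or more | 0% | 0% |

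The VTE rule also counts the index day itself. That adds at most one day and does not alter the picture. With the windows placed at the OAC start, both columns would read 100% at every t.

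**Step 3: criterion 6.** It acts on one day. It screens a dual start at t = 0 and none at t ≥ 1.

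**Step 4: does anything else cover the gap?**
- Section 8.2 ends follow-up at death, disenrollment, switch, discontinuation or study end. A VTE or joint replacement after index is not on the list.
- The weights in 8.7 name comorbidities in general, the CHA2DS2-VASc score and bleeding history, in an open-ended list. VTE and joint replacement are not named.
- None of the analyses in 8.8 concerns VTE or surgery. Censoring at 6 months shortens the possible delay, but a start between day 42 and month 6 is still unscreened for joint replacement.

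**The case against.** **Eligibility belongs at time zero.** Follow-up starts at AF diagnosis and treatment is time-varying, so fixing eligibility at index is normal. Excluding patients at baseline for a later VTE or operation would condition on the future. This stands, and it is why the index-date exclusions should be kept. It does not answer the question of what happens to a VTE or operation between index and OAC start.

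**Exposure is defined by claim.** A reader might infer that OAC begun after a VTE or operation is misclassified exposure. The documents do not support that: the objectives compare patients treated and untreated with OACs, and 8.2.3 asks only for a claim. Such a patient is on an OAC, and after a VTE the drug may serve both indications. The defect for the secondary objectives is time-varying confounding.

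**The weights could take it in.** The covariate list is open-ended and left to clinical rationale, and a full list may properly sit in the SAP. Post-index VTE or surgery could be included. This softens the point, but the protocol fixes windows that do not reach later starts and does not name the covariates that would stand in for them.

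**Dual fills may already be censored.** Table 2 counts a non-index anticoagulant filled within 30 days either side of run-out as a switch, and 8.2 ends follow-up at a switch. For a first supply of S days, a same-day second drug is filled S days before run-out, so it is caught when S ≤ 30. Longer supplies are not, and nothing says which of two same-day drugs is the index drug. Such patients are probably few.

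**Limits are acknowledged.** Section 8.10 concedes residual confounding and claims only associations, and 8.7 makes the secondary objectives optional. Neither is a reason to leave a cheaply repaired gap open.

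**Conclusion.** The point holds. Three stated rules are anchored at a date that can precede the start of treatment by up to 1,460 days. The hip/knee rule screens nothing before OAC starts at 42 days or later, the VTE rule nothing before starts at 365 days or later, and criterion 6 nothing after the index day. These results need only the protocol's own dates and windows. That the mismatch matters rests on two inferences: the purpose of the exclusions, and the expectation that risk and cost differ just after a VTE or operation.

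The size of the bias cannot be computed, because the documents give neither the distribution of delays nor the frequency of post-index VTE or joint replacement. A reader might try to size it from assumed rates. For example, suppose that among untreated patients 5–15% per year start OAC for AF and 1–3% per year start after a VTE or joint replacement. The share of late starts affected is then 1/(1+15) = 6% to 3/(3+5) = 38%, with 17% if low is paired with low (1/6) or high with high (3/18). Those rates are in neither the protocol nor any source at hand. The result also concerns late starts only, so the share of all treated patients or treated time is smaller by an unknown amount. It should not be quoted as an estimate.

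The direction is also open: for cost, part of the care for the event may fall in untreated time and part in treated time, depending on the fill date.

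For the primary objective the issue is narrower. Because 8.2.1.2 has no VTE or surgery exclusion, patients with a VTE already present at index enter the treated proportion and the odds ratios. That fits the claim-based definition but affects interpretation, so a sensitivity analysis is enough.

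**What to change.** 1. **Criterion 6.** Apply it on the first OAC fill date, which is the OAC prescription index date of Table 2. Censor dual starters at that date; do not remove them at baseline for a later event.
2. **Weights.** Keep the VTE and hip/knee exclusions at index for eligibility. In 8.7, name post-index VTE and post-index hip/knee replacement as time-dependent covariates in both the treatment and the censoring weights.
3. **Secondary sensitivity analysis.** In 8.8, add an analysis that censors every patient, whatever the treatment status, at the first post-index VTE or hip/knee replacement. State that OAC may itself affect the risk of VTE, so this censoring may depend on treatment and needs the censoring weights. For that reason it should not be the main analysis.
4. **Primary sensitivity analysis.** Apply the same VTE and hip/knee exclusions at index. Do not reclassify later OAC starts: a patient whose OAC claim is set aside would be neither ever-treated nor never-treated under 8.2.3.

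The cost is protocol wording, reuse of code definitions that the exclusions already require, somewhat more analysis work, and some lost follow-up in the sensitivity analysis in item 3.

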# 8.2.3. Cohorts

Patients eligible according to the above criteria will be assigned to the following cohorts:

Do not distribute for purposes outside of specific activities related to development of FDAMAs114 compliant pieces. Content within this protocol is subject to change based on communication planning and input by external review committees.

Apixaban NON-INTERVENTIONAL STUDY PROTOCOL

- 1) Ever-Treated Cohort: NVAF Patients had ≥1 pharmacy claim for apixaban, dabigatran, edoxaban, rivaroxaban, or warfarin from 01JAN2013-31DEC2016 on or after the first AF diagnosis
  - a. Apixaban cohort: Patients who initiated with apixaban on or after index date
  - b. Dabigatran cohort: Patients who initiated with dabigatran on or after index date
  - c. **Edoxaban cohort:** Patients who initiated with edoxaban on or after index date. Given the small sample size, edoxaban patients will not be included in the secondary clinical and healthcare utilization and costs analyses.
  - d. Rivaroxaban cohort: Patients who initiated with rivaroxaban on or after index date
  - e. Warfarin cohort: Patients who initiated with warfarin on or after index date
- 2) Never-Treated Cohort: NVAF patients with no pharmacy claim for an OAC from 01JAN2013-31DEC2016

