# 8.2. Setting

Ever treated with OAC and never treated with OAC patients will be selected from 01JAN2013-31DEC2016. To ensure access to the patients' complete medical history, they will be required to have continuous health plan enrollment for the 12 months before the first AF diagnosis date/index date (baseline period). Patient data will be assessed from index date until the earliest of death, health plan disenrollment, treatment switch (treated patients), discontinuation (treated patients), or 31DEC2016 (end of study).

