#### Apixaban

Table 2. Clinical and Treatment Pattern Outcome Variables					
Variable	Role	Operational Definition			
Stroke/SE	Outcome	Stroke/SE will be identified using hospital claims with a stroke/SE diagnosis code as the first listed ICD-9-CM or ICD-10-CM code. Stroke/SE will be classified into 3 categories: ischemic stroke, hemorrhage stroke, and SE. Time to stroke/SE will be defined as the number of days from index date to the occurrence of the first stroke/SE requiring hospitalization.			
Major bleeding	Outcome	Major bleeding will be identified using hospital claims with a bleeding diagnosis code as the first listed ICD-9-C or ICD-10-CM diagnosis or procedure code.  Time to major bleeding will be defined as the number of days from index date to the occurrence of the first major bleeding event requiring hospitalization. Major bleeding may be further stratified by gastrointestinal and intracranial hemorrhages and other major bleeding.			
Death	Outcome	Death information from the database will be used. Time to death will be defined as the number of days from index date to death.			
Discontinuation (Treated Patients)	Outcome	Treated patients will be considered to have discontinued if there was no additional refill for the index anticoagulant after 30 days of the previous prescription's run-out date.  The discontinuation date will be defined as the run-out date plus 30 days.			
Time to discontinuation (Treated Patients)	Outcome	Time to discontinuation will be defined as the number of days from the OAC prescription index date to the discontinuation date.			
Switch among anticoagulants (Treated Patients)	Outcome	A switch among anticoagulants will be defined as a prescription filled for non-index anticoagulants within 30 days before or after the run-out date.  Time to switch will be defined as the number of days from the OAC prescription index date to the first prescription date of the switch.			
Time-to-switch (Treated Patients)	Outcome	Time to switch will be defined as the number of days from the OAC prescription index date to the switch date.			

Table 2, Clinic	cal and Treatment Patt	ern Outcome Variables
	cal and frequencine i acc	

Do not distribute for purposes outside of specific activities related to development of FDAMAs114 compliant pieces. Content within this protocol is subject to change based on communication planning and input by external review committees.

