# 8.4. Data Sources

#### Medicare Inpatient Data

The inpatient claim file contains final action claims data submitted by inpatient hospital providers for facility cost reimbursement. Information therein includes ICD-9-CM diagnosis and ICD-9 procedure codes, ICD-10-CM diagnosis and ICD-10 procedure codes, Diagnosis Related Groups, dates of service, reimbursement amounts, hospital providers, and beneficiary demographic information. All file observations are at the claim level.

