# Medicare PDE Data

The Medicare PDE data contains prescription drug costs and payment data that enable CMS to make payments to the plans and otherwise administer Part D benefits. When a beneficiary fills a prescription under Medicare Part D, a prescription drug plan sponsor must submit a summary record to CMS. Unlike individual drug claim transactions, the PDE data are summary extracts using CMS-defined standard fields.

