# Skilled Nursing Facility

The SNF file contains final action FFS claims data submitted by SNF providers. This file includes ICD-9-CM and ICD-10-CM diagnosis and procedure codes, dates of service, reimbursement amount, SNF provider number, and beneficiary demographic information.

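### OAC start is seen only through a Part D fill while the death clock can start in hospital, so facility deaths before a first fill count as untreated and bias the death comparison towards OAC

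*Protocol*

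**What the plan says.** - **Entry and time zero.** Protocol 8.2.1.1 admits a patient on a single inpatient AF claim and makes the first AF claim date the index date. It does not say whether an inpatient claim is dated at admission or at discharge.
- **Clock.** Section 8.2: "Patient data will be assessed from index date until the earliest of death, health plan disenrollment", among other end points. Table 2: "Time to death will be defined as the number of days from index date to death".
- **Exposure.** Section 8.2.3 requires at least one "pharmacy claim for apixaban, dabigatran, edoxaban, rivaroxaban, or warfarin from 01JAN2013-31DEC2016 on or after the first AF diagnosis". The drug source described in 8.4 is Part D: "When a beneficiary fills a prescription under Medicare Part D, a prescription drug plan sponsor must submit a summary record to CMS". The other files are described differently: "The inpatient claim file contains final action claims data submitted by inpatient hospital providers for facility cost reimbursement", and "The SNF file contains final action FFS claims data submitted by SNF providers". Neither description lists drug dispensing.
- **Attribution.** Section 8.7: "Treatment will be used as a time varying covariate". The abstract adds that ever-treated patients contribute their time off treatment to the untreated side. Under Table 2, once a patient has filled, treatment lasts to the run-out date plus 30 days.
- **Safeguards.** For the secondary objectives, 8.2.2 excludes follow-up of 0 days. The abstract ties the 6-month post-index enrolment rule to the primary objective and the high-risk subgroups.

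**The concern.** A patient diagnosed with AF during an admission is at risk of death from the index date but cannot show a pharmacy fill until leaving. If OAC is started on the ward and the patient dies there, the plan records an untreated death. These days carry high mortality and offer no observable route into the treated state. That is a positivity failure: the probability of an observed start is zero, so no inverse-probability weight built on it can rebalance the comparison.

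All five contrasts in section 7 (any OAC, apixaban, dabigatran, rivaroxaban and warfarin, each against untreated) share this exposure rule, so the error favours every OAC. A spurious survival benefit would also fit the expectation in section 6 that untreated patients survive less well, and so might pass unquestioned.

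**Working it through.** **No plan figure to reproduce.** Section 8.5 sizes stroke/SE and major bleeding only and gives nothing for death. All rates below are assumptions, shown as a range.

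**Inputs (low / mid / high)**
- inpatient index p: 25 / 40 / 55%
- death per hospital stay h: 3 / 5 / 8%
- mean hospital stay: 5 / 6 / 7 days
- discharge to SNF s: 15 / 20 / 30%
- death per SNF stay q: 4 / 7 / 12%
- mean SNF stay: 25 / 25 / 28 days
- community mortality c: 12 / 10 / 8% per year

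**Step 1: deaths that cannot be treated deaths, per 1,000 patients, ignoring readmissions**

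Hospital deaths = 1000·p·h. SNF deaths = 1000·p·(1−h)·s·q. Community deaths by 6 months = (1000 − facility deaths)·(1 − (1−c)^0.5).

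| | Low | Mid | High |
|---|---|---|---|
| Index-stay deaths | 250×0.03 = 7.5 | 400×0.05 = 20 | 550×0.08 = 44 |
| SNF deaths | 242.5×0.15×0.04 = 1.5 | 380×0.20×0.07 = 5.3 | 506×0.30×0.12 = 18.2 |
| Facility total | 9.0 | 25.3 | 62.2 |
| Community deaths, 6 months | 991.0×0.0619 = 61.4 | 974.7×0.0513 = 50.0 | 937.8×0.0408 = 38.3 |
| Facility share of 6-month deaths | 13% | 34% | 62% |

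Facility days per 1,000 patients:
- low: 250×5 + 242.5×0.15×25 ≈ 2,160
- mid: 400×6 + 380×0.20×25 = 4,300
- high: 550×7 + 506×0.30×28 ≈ 8,100

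Against 1000×182.5 = 182,500 patient-days, these are about 1.2%, 2.4% and 4.4%. A small part of follow-up therefore holds a large part of the early deaths, all of them on the untreated side.

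**Step 2: dependence on the two unstated points.** If the index is the discharge date, index-stay deaths have 0 days of follow-up and are excluded. Only the SNF deaths remain: 1.5/(1.5+61.4) = 2%, 5.3/(5.3+50.0) = 10% and 18.2/(18.2+38.3) = 32% of the deaths counted. If SNF stays do produce Part D fills, only the index-stay row applies. If both hold, this route closes.

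**Step 3: hazard ratio for death when OAC has no effect.** This is a simulation in daily steps with the inputs above, 45% never treated, readmission 35 / 40 / 45% per year, mean time to first fill 7 to 45 days, and an unweighted Cox model with time-varying treatment. A first fill is possible only outside a facility. There is no discontinuation.

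| Horizon | Low | Mid | High |
|---|---|---|---|
| 6 months | 0.87-0.93 | 0.72-0.86 | 0.52-0.70 |
| 2 years | 0.96-1.00 | 0.90-0.97 | 0.80-0.90 |

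The control, identical except that a start is visible in any setting, returns 0.98-1.02. The departure from 1 therefore comes from fill-only recognition.

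**Step 4: what adjustment and a later start achieve.** Some of the departure in Step 3 arises because inpatient entrants both die earlier and fill later. Stratifying on entry setting, with assumed inputs of the same kind, leaves about 0.95-0.69 at 6 months and 0.98-0.90 near 3 years. Starting follow-up at facility discharge returns about 0.98-0.99. A separate one-year null simulation assumed 30-50% inpatient index, 2-6% in-hospital mortality, 0-40% going on to SNF, and 55% starting OAC a mean of 10 days after facility discharge. It gave 0.81-0.92 from the index date, 0.88-0.96 stratified on entry setting, and 0.98-1.01 from facility discharge.

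**Step 5: the protocol's own checks.** Baseline variables exclude the index date, and Table 1 has no entry-setting variable. The examples of time-dependent weight covariates in 8.7 do not name facility status. The 6-month censoring analysis in 8.8 keeps the affected days and discards the later follow-up that dilutes them. In Step 3 it moves the mid case from 0.90-0.97 to 0.72-0.86.

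**The case against.** A reader might infer that every death in a hospital or SNF is charged to untreated time. The documents do not support this. Under Table 2, a patient who has filled stays treated to run-out plus 30 days, so a death in a later stay within that window counts as treated. In Step 3, 12-39% of facility deaths fell in treated time. This is an upper-end share, because that model has no discontinuation. The point holds only for deaths before a first fill.

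A reader might also take it as fixed that nobody in a facility can become treated. For hospital stays the file descriptions support this. For SNF stays the protocol states no billing rule, so it is an assumption. The index-stay part further depends on the admission-or-discharge question, which an SAP might settle.

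The planned analysis is weighted and its covariate list is open, whereas the models above are unweighted. The hazard ratios are therefore illustrations, not forecasts of the study's result. That limits the size, not the mechanism, since a zero probability of start cannot be weighted away.

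Section 8.2.2 could be read as inheriting the 6-month post-index enrolment rule, which would remove early deaths. The abstract limits that rule to the primary and subgroup analyses, and a separate exclusion for 0 days of follow-up would be pointless if it applied.

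Finally, 8.7 makes the secondary objectives optional, and 8.10 concedes incomplete claims data, residual confounding and association only. These are general cautions. None identifies or removes this error.

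**Conclusion.** The point stands in limited form. Deaths in the index hospital stay before a first fill count as untreated if the index is dated at admission. Deaths in a directly following SNF stay do so too if such stays yield no Part D fill. The death comparison is then biased towards OAC, and the weights cannot correct it.

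A working range under no true effect, after allowing for entry setting, is a hazard ratio of about 0.7-0.95 at 6 months and 0.9-1.0 over 2-3 years. The most adverse unstratified assumptions go lower, and the mildest are negligible over long follow-up. None of the inputs is in the protocol, so no single figure can be attached to the plan.

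By the same logic, a bleed arising in a SNF while OAC is given there would be charged to untreated time. That is direction only: it rests on the SNF assumption and was not quantified.

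**What to change.** In section 8.2 and Table 2, for the secondary clinical outcomes:

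1. State which date of an inpatient AF claim is the index date.
2. When the index claim is inpatient, start follow-up at live discharge from that stay, extended to the end of a directly following SNF stay. Use this as the main rule or as a prespecified sensitivity analysis.
3. Stratify on, or adjust for, inpatient versus outpatient entry.
4. Report deaths before the new start date separately.
5. Apply the same start to the 6-month censoring analysis in 8.8.

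The cost is wording and programming, since the inpatient and SNF files already carry dates of service. The downside is small: the estimate applies to patients discharged alive.

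Do not extend this by stratifying risk sets on later in-facility status. That status arises after treatment starts and can lie on the path from OAC to death. Stroke/SE and major bleeding are themselves defined by hospitalisation.
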